3.3.2. Adherence and safety monitoring

To ensure participants' adherence to their medication and monitor safety, participants will be informed on how to take their medications, about the side effects of the treatment and the importance of compliance to the treatment. In addition to DOT on day 0, The VMW will conduct a day

3, day 7, and day 14 adherence and safety monitoring visit for all individuals treated with primaquine for *P. vivax*, and the VMW will ask a series of questions to determine adherence with each dose, number of remaining tablets, potential adverse events, and reasons for non-adherence or treatment refusal. Participants with phone number will be sent a daily text message to remind them to adhere to their treatment and remind them about any symptoms suggesting serious adverse events. All participants and their family members will be provided a chart to record and track their adherence as well as symptoms that may indicate an adverse event.

The safety risks associated with participation in this trial are expected to be minimal. The study drugs, AL and PQ, are well tolerated first-line treatments and safe for G6PD non-deficient individuals. Prior to drug administration, participants will be asked about known contraindications, and if such contraindications are reported, participants will be restricted from taking the medication.

Drug	Contraindications
AL	Pregnancy, infants < 5kg, prior allergic reaction, any severe disease
PQ	Pregnancy, age < 12months, infants < 10kg, women in first 12 months of breastfeeding, prior allergic reaction, any severe disease, G6PD deficient

The common adverse events reported for each drug are as below:

- AL: headache, dizziness, loss of appetite, generalized weakness, fever, chills, arthralgia, myalgia, nausea, vomiting, and abdominal pain
- PQ: nausea, headache, fatigue, dizziness, hives, chest pain, painless darkening of urine, jaundice of skin and vomiting.

The Primaquine Roll Out Pharmacovigilance Tool Data Collection Forms (PROMPT) will be used to track the status of individuals treated with PQ. Identification of serious adverse events (SAEs) will occur both passively and actively. As part of the consent process, participants will be instructed to call or visit VMW to report any adverse events that occur between VMW visits. During adherence and follow up visits, the VMW will also ask participants for specific adverse events related to hemolysis. SAEs as well as serious unexpected serious adverse reactions (SUSAR) will be reported to the study management and PI who will report to the data safety monitoring board (DSMB). At each study site, a local physician will be recruited (Local Safety Monitor, LSM) to determine causality and grade of the SAE. All SAEs will be reported to the Pharmacovigilance center of the Ministry of Health (Lao PDR) and the respective IRBs. All potential AEs or SAEs will be referred by VMW to the nearest health center or district hospital for management and documented as per 4.2 below, and the study will reimburse all patient travel and hospitalization resulting from study drug administration.

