All individuals who test positive by either HS-RDT or Standard RDT will be told of their results and treated on site per national guidelines:

- Individuals with *P. falciparum* infection will be treated with an age-appropriate course of artemether-lumefantrine (AL) and a single low dose of primaquine (SLD-PQ). Weight-based dosing is described in Tables 2 and 3 below.
- At all study sites in Lao PDR, patients with a *P. vivax* infection identified by RDT (both febrile and asymptomatic) will be given a unique coded and signed informational letter directing them to the nearest district hospital (or other testing facility) for G6PD deficiency testing and possible radical cure administration depending on results. Study contact information will also be included if the participants present at other health facilities. At the health facility, G6PD normal individuals will be treated with AL and a 14-day course of PQ, whereas G6PD deficient individuals will receive AL alone as per the national guidelines and referred to a hospital for further primaquine management decisions. The study staff will meet with district hospital and health facility staff monthly from all study areas and nearby district hospitals and health facilities to collect these forms, with small incentives for health staff to report receiving a study card (phone top up card, etc.) to maximize data completeness. After six months of implementation, a subset of VMWs will begin conducting qualitative G6PD testing and treatment administration at the community-level with the assistance of a health facility staff member.

Table 2. AL weight-based dosing

Body weight (kg)	Tablet strength (mg)		Tablets/dose	Mg of drug per dose		Tablets/day
	Artemether	Lumefantrine		Artemether	Lumefantrine	
5 to 14	20	120	1	20	120	1 tablet given twice* per day for 3 consecutive days

15 to 24	20	120	2	40	240	2 tablets given twice* per day for 3 consecutive days
25 to 34	20	120	3	60	360	3 tablets given twice* per day for 3 consecutive days
35 or greater	20	120	4	80	480	4 tablets given twice* per day for 3 consecutive days
*Approx. 8 hours between doses 1 and 2. Approx. 12 hours between all other consecutive doses.						

Table 3. Weight-based dosing of SLD- Primaquine (.25 mg/kg) for *P. falciparum*

Body weight (kg)	SLD-PQ dose (7.5 mg tablet) (as base)	Tablets
10 to < 25	3.75	1/2
25 to < 50	7.5	1
50 to 100	15	2
*Given as SLD in addition to AL for P falciparum positive		

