3.4.3.2. Primary outcomes measures

1. Population coverage of enhanced RACD interventions: this indicator will be measured in two ways. Operational program coverage will be defined as the proportion of individuals ≥ 18 months old and households visited and offered the RACD interventions within the target areas per time period. Effective program coverage is defined as the proportion of individuals (≥ 18 months old) that agreed to participate in the RACD intervention among all individuals ≥ 18 months old eligible to participate in the intervention in the target population per time period.
2. Feasibility of conducting enhanced RACD intervention at the community level: feasibility will be determined based upon a combination of population coverage data, responses of provincial, district, and health staff, VMWs, and community members to KIIs and FGDs at baseline and endline, VMW competency checklists at baseline, midline, and endline, and cost data.
3. Acceptability of community-based RACD approaches: acceptability will be determined based upon refusal rates during interventions and responses of community members and VMWs to endline questionnaire, interviews, and focus groups.
4. Safety of community-based RACD and treatment follow-up: safety measures will include the adverse event rate amongst treated individuals and hemoglobin measurement pre and post treatment for individuals receiving PQ.
5. Operational feasibility of G6PD referral: operational feasibility of G6PD referral will be determined by the results of the process-mapping and co-design workshops at baseline, responses of health staff and VMWs to interviews and focus groups at baseline and endline and competency checklists at baseline, midline, and endline, the proportion of referred *P. vivax* cases presenting at a health facility for G6PD testing, and the proportion of *P. vivax* cases with a valid recorded G6PD result.
6. Assessment of *P. vivax* treatment adherence: treatment adherence will be determined by the proportion of *P. vivax* cases with physical evidence of adherence through pill count, the *P. vivax* relapse rate across study arms, and the proportion of *P. vivax* cases with successful parasite clearance on day 14.

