The adverse event rate for RDT positive participants will be assessed using intervention data and health facility adverse event reporting forms. Study staff and VMWs will be trained on detection of adverse events for positive cases receiving treatment.

Outcome 5: Operational feasibility of G6PD referral, testing and non-adherence

The operational feasibility of G6PD referral, testing and non-adherence at the community and facility levels will be evaluated. For testing, interview data at baseline and endline will be collected from district health staff and community members, as well as focus group discussions with both groups at end-line. Risk factors for non-adherence to G6PD testing after referral will be determined through comparison of factors captured at enrollment for individuals who were tested at a facility versus those who were not.

Outcome 6: Assessment of *P. vivax* treatment adherence

The treatment adherence of *P. vivax* positive study participants will be assessed through physical evidence of adherence during VMW follow-up visits on day 3, 7 and 14 and comparison of relapse rates across study arms.

3.4.4. Assessment of the risk of malaria vector biting in forest and village settings

A baseline entomological investigation will be conducted along with the baseline qualitative activities in Aug/Sep 2019. The investigation will involve collection of vector occurrence and density data (by species), human landing catches (HLC) to assess vector biting behaviors (indoor vs outdoor and forest sites), and household structure type, and human behavioral observations. All collections will take place over a one-week period. HLC collections will occur in 4-5 sleeping structures each in the forest and village, with 2 HLC collectors by structure. At the end of each HLC collection hour, collectors will also record human behavior (sleeping (or awake) under net/sleeping without net/awake), both indoors and outdoors. Field collectors will be community volunteers that will have been properly informed about the sampling methods and their implications, and who have consented to participating by signing consent forms. Prior to the start of collections, volunteers will also need to be tested for malaria. Depending on national policy, they may also be required to take malaria prophylaxis. HLC data collection forms are found in the Appendix.

4 Ethical issues related to human subjects research

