A passive case detection system will be employed in both intervention and control villages to help detect and refer any potential SAEs and active follow-ups will be conducted by VMWs on days 3, 7, and 14; VMWs/VHVs will be oriented on potential drug side effects and asked in addition to passively monitor their communities and refer any potentially serious or unexpected AEs. All public health facilities in the nine target districts will be trained on AE reporting procedures prior to implementation of any study activities. A data safety monitoring board (DSMB) will be established to oversee and report on any SAEs that are potentially linked to the administration of AL or SLD-PQ, as outlined in further detail in Section 4.5. The following steps will be taken for all AEs:

The health facility will complete an AE reporting form (Appendix 8.14). The completed form will then be submitted to the Local Safety Monitor (a medical doctor), who with the support of the UCSF project manager will assess if the event is an SAE or unexpected AE based upon specific criteria determined by the DSMB. If determined to be an SAE or unexpected AE, the UCSF project manager will submit the AE reporting form and any accompanying documentation (clinical records, laboratory reports) to the DSMB and the UCSF PI within 48 hours from the identification of the potential SAE.

Upon receipt of the AE reporting form, the DSMB will complete an AE investigation form (Appendix 8.14) within 24 hours to a) confirm if the event is an SAE, and 2) to determine if the SAE was caused by the administration of AL with SLD-PQ as part of this study. If the event is confirmed to meet the criteria of an SAE, the DSMB will submit the completed AE investigation form to the PI, who will submit to the research ethics committees (RECs) at UCSF and NIOPH. The respective RECs will be notified within 24 hours of the DSMB's completion of all potential SAE investigation forms, and within 48 hours of DSMB notification if deemed an AE, but not fulfilling criteria for an SAE.

Travel and hospitalization costs for any SAEs resulting from PQ administration will be covered by the study.

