5.1. Potential risks from participation

Detailed discussion of potential AEs related to drug regimens is discussed above in section 4.2. Finger pricks for RDTs and DBS are associated with small risks of bleeding, hematoma, and infection. To minimize these risks, the skin will be cleaned with alcohol prior to puncture, and sterile unused lancets will always be used, and pressure will be placed on the puncture site after removal of the lancet using sterile gauze. Although the quantity of blood drawn would not lead to any ill effects on the participants' health, some adults and rarely children feel faint from the blood during the finger prick. The risks will be minimized by having trained health staff perform all procedures, and all untoward effects will be evaluated by health center staff.

For those subjects with *P. vivax* diagnosis that are tested for G6PD deficiency, there is a risk of misclassification and wrongly ascribed to being G6PD non-deficient and then being treated with 14 days of PQ. In this study, the team will ensure a high-quality of training for all those using the G6PD RDTs, in addition subjects will be given information on what to do if they experience adverse events, and on days 3 and 14 all subjects given PQ will be actively followed up. If hemolysis is suspected PQ treatment will be stopped and the subject monitored to at least day 14. Should the hemolysis event require further clinical management, the study team will ensure access to appropriate health services.

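### The pooled adverse event rate mixes visited and unvisited regimens, pre/post hemoglobin has no described collection step, and section 5.1 omits the day 7 visit

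*Protocol*

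**What the plan says.** **Who is visited, and when.** Section 3.3.2 sets a day "3, day 7, and day 14 adherence and safety monitoring visit for all individuals treated with primaquine for *P. vivax".

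Section 4.2 says that "active follow-ups will be conducted by VMWs on days 3, 7, and 14" and names no group. The evaluation table in 3.4.1 and Outcome 6 in 3.4.3.5 repeat days 3, 7 and 14 when they describe adherence. Section 5.1 differs: "on days 3 and 14 all subjects given PQ will be actively followed up".

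**Who receives primaquine.** Section 3.3.1 states: "Individuals with *P. falciparum* infection will be treated with an age-appropriate course of artemether-lumefantrine (AL) and a single low dose of primaquine (SLD-PQ". G6PD-normal P. vivax patients receive AL and the 14-day course. G6PD-deficient P. vivax patients, and people with a contraindication to primaquine, receive AL alone.

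**What is measured.** Section 3.4.3.2 says that "safety measures will include the adverse event rate amongst treated individuals and hemoglobin measurement pre and post treatment for individuals receiving PQ". The matching analysis text in 3.4.3.5 reads: "The adverse event rate for RDT positive participants will be assessed using intervention data and health facility adverse event reporting forms". At the follow-up visits, according to 3.3.2, "the VMW will ask a series of questions to determine adherence with each dose, number of remaining tablets, potential adverse events" and reasons for not taking the drug.

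**The concern.** The trial has a stated secondary objective on the safety of G6PD testing and primaquine given in the community. The risk of interest is hemolysis during a 14-day course. Three features of the text weaken the measures meant to address it.

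- The adverse event rate has a wider denominator than the group that is actively questioned. Events in 14-day recipients are sought at three visits. Events in everyone else come to light only if the patient reports them or a worker happens to notice. One rate over both groups answers no clear question about either regimen.
- Hemoglobin is the more objective marker of hemolysis, but the text assigns the measurement to nobody. A pre-treatment value that is not taken cannot be recovered later.
- A reader of section 5.1 alone would schedule no visit between days 3 and 14 of the course, although 3.3.2 requires one on day 7.

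**Working it through.** The protocol states no safety figure that could be reproduced, so the check is a comparison of the text.

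**1. Visit days and population**

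| Place | Days | Group named |
|---|---|---|
| 3.3.2 | 3, 7, 14 | treated with primaquine for P. vivax |
| 3.4.1 table, adherence row | 3, 7, 14 | P. vivax RDT-positive cases |
| 3.4.3.5, Outcome 6 | 3, 7, 14 | P. vivax-positive participants |
| 4.2 | 3, 7, 14 | none |
| 5.1 | 3, 14 | all given PQ, in a paragraph about P. vivax |

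Four statements agree on the days and one omits day 7. The group needs naming because the document uses PQ loosely. Section 3.3.1 separates the single low dose from the 14-day course, whereas sections 2.6 and 4.2 call the single dose PQ as well.

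**2. Ascertainment by regimen, if 3.3.2 governs**

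| Regimen | Scheduled safety visits | Other routes |
|---|---|---|
| AL + 14-day PQ | days 3, 7, 14 | all routes below |
| AL + single low-dose PQ | none | self-report, symptom chart, text messages if the patient has a phone, passive detection, PROMPT forms |
| AL alone | none | self-report, symptom chart, text messages if the patient has a phone, passive detection |

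The PROMPT forms "will be used to track the status of individuals treated with PQ", but no contact schedule is attached to them.

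Let w be the share of treated people with no scheduled visit. Let p1 and p0 be the true event risks with and without scheduled visits, and a and b the probabilities that an event is recorded in each group. Then

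pooled recorded rate = (1 − w)·a·p1 + w·b·p0.

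If the true risks are equal (p1 = p0 = p), this becomes p·[a − w·(a − b)]. Unless a = b, the rate moves with w even though risk is constant. If b is below a and the single dose is no riskier than the long course, the pooled rate lies below the rate recorded in 14-day recipients, so it dilutes the estimate that the objective needs.

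The mix w need not be stable. In Table 1 the P. falciparum share of routine cases is 0.65/13.76 = 5% in Samouay and 16.6/18.25 = 91% in Taoi. These are routine cases, not people treated during RACD, so they show only that the mix varies.

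**3. Hemoglobin**

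| Step described | Hemoglobin listed? |
|---|---|
| RACD sampling, household and co-worker (3.3.1): two RDTs, four blood spots | no |
| Health facility step for P. vivax (3.3.1): G6PD test, then treatment | no |
| Worker visits (3.3.2): questions, tablet count | no |
| Safety analysis, Outcome 4 (3.4.3.5) | no |
| Endline household survey (3.4.2.5.2): Hemocue kit | yes, but not tied to treatment |

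No time point, device or responsible person is given for the measurement promised in 3.4.3.2.

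**The case against.** A reader might infer that the protocol sets three competing schedules. It does not. Section 4.2 gives the same days as 3.3.2 and is merely silent on the group. Section 5.1 sits in a paragraph about P. vivax patients and probably means the same people. What remains is one missing day in a risk summary and a group that should be named.

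Active visits for the 14-day course, with passive detection for a single low dose that the protocol regards as safe without G6PD testing, is a risk-proportionate choice. That stands, and the follow-up intensity is not the criticism. The evaluation table in 3.4.1 also places the adverse event rate under an objective about P. vivax treatment, and a breakdown by regimen could be set out in an analysis plan. But 3.4.3.2 and 3.4.3.5 themselves fix the denominator as treated or RDT-positive people, which is wider than that objective.

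A reader might also infer that hemoglobin will not be collected at all. The documents do not show that. P. vivax patients mostly start treatment at a facility, where a value could be taken, and the G6PD register, adherence and PROMPT forms (appendices 8.12, 8.24, 8.25) are listed but not available here. The supportable statement is that the text describes no collection step.

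Finally, a percentage for the understatement is tempting. It would need the detection ratio b/a, which the documents do not give. It would also need the regimen mix among RACD-treated people, which may differ from Table 1 because the HS-RDT in use detects P. falciparum only.

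**Conclusion.** The point holds as a minor one. The adverse event rate as defined pools people with different ascertainment and cannot be read as the safety of 14-day primaquine. This rests on 3.3.2 being the operative visit rule and on visits finding more events than passive reporting. The promised hemoglobin measure has no described procedure. Section 5.1 conflicts with the rest of the protocol on day 7 under any reading of who is visited.

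No numerical size can be given from the documents. The effect is confined to secondary safety outcomes. It is not evidence that individual patients are unprotected: passive detection, referral, review by the Local Safety Monitor and oversight by the safety board all remain in place.

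**What to change.** 1. In 3.4.3.2 and 3.4.3.5, report the adverse event rate separately for AL + 14-day PQ, AL + single low-dose PQ and AL alone, and state the mode of ascertainment for each. This uses data already collected. The cost is smaller denominators, hence less precise rates per regimen.
2. Either schedule hemoglobin for 14-day PQ recipients at treatment start and at one named existing visit, with the device and the responsible person stated, or remove it as a safety measure. If it is kept, the cost is two tests per recipient and no extra visit. Because some village workers begin testing and treating after six months, the text should cover starts both at the facility and in the village.
3. Add day 7 to section 5.1, and name 14-day PQ recipients as the visited group in 4.2 and 5.1. This is wording only.

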3.4. Study evaluation methods

3.4.1. Overview of evaluation activities by study objectives, outcomes, and data collection activities

Table 4. Overview of evaluation activities

Study activity	Research objective	Primary outcome measures	Data collection activity
Activity 1: Impact evaluation of enhanced RACD	1. Evaluate the relative effectiveness of enhanced community-based RACD using HS-	Total confirmed outpatient (OPD) P. falciparum and P. vivax malaria case incidence among all ages by health facility catchment	Routine malaria data from all reporting VMWs, health centers and district hospitals

	RDTs in villages and forest-based HRPs, compared to control	P. falciparum and P. vivax prevalence in all individuals	Cross-sectional parasite survey November-December 2020	
		HS-RDT and RDT test positivity rate	HS-RDT and RDT positivity data from RACD intervention data	
Activity 2: Assessment of the feasibility and acceptability of community-based RACD	1. Assess the operational feasibility of community-based RACD	Population coverage of RACD and interventions	RACD intervention data	
		Proportion of VMWs who rate conducting the RACD interventions as very easy, somewhat easy, somewhat difficult, and very difficult, and changes in proportions over time	Entrance, mid-intervention, and exit competency checklists with VMWs; focus group discussion and interviews with VMWs at end-line	
		Costs of RACD as unit and total costs; cost-effectiveness will be assessed as an incremental cost effectiveness ratio (ICER)	Program data on costs combined with estimates of program effectiveness	
	2. Assess the acceptability of community-based RACD	Proportion of targeted individuals refusing RACD intervention	RACD intervention data	
		Proportion of survey respondents who strongly disagree, disagree, are ambivalent, agree and strongly agree on the importance and acceptability of community-based RACD	Cross-sectional survey and qualitative studies at endline with villagers, forest workers, VMWs and other health sector staff	
Activity 3: Assessment of the operational feasibility and safety of conducting G6PD testing, referral, and treatment adherence among positive P. vivax RDT cases	1. Assess the operational feasibility of G6PD referral at community level	Proportion of VMWs who rate conducting G6PD referral as very easy, somewhat easy, somewhat difficult, and very difficult, and changes in proportions over time	Entrance, mid-intervention, and exit competency checklists with VMWs; focus group discussion and interviews with VMWs at end-line	
		Proportion of P. vivax cases with valid recorded G6PD result	VMW and health facility records	
	2. Determine risk factors for non-attendance at hospitals or health centers after referral for G6PD testing	Proportion of referred cases presenting at hospitals or health centers for G6PD testing.	Cross-sectional survey and qualitative studies at endline with villagers, forest workers, VMWs	
	3. Assess treatment adherence among positive P. vivax RDT cases	Proportion of patients with physical evidence of full adherence with the prescribed drug regimen	VMW follow-up visits on day 3, 7, and 14	
		Proportion of P. vivax cases who relapsed in the six months following treatment	VMW and health facility records	
	4. Assess the safety of community-level G6PD testing, referral, and P. vivax treatment follow-up	Adverse event rate per treated individual	RACD intervention data and VMW follow-up visits; health facility adverse event reporting forms	
	Activity 4: Assessment of the risk of malaria vector biting in forest and village settings	1. Describe local vector species composition and bionomics in forest and village settings	Vector occurrence and density by species; vector biting behaviors; human behavioral observations in relation to human biting rate (HBR)	Human Landing Catches (HLCs) vector sampling at baseline

